9.9. Contraception Requirements and Pregnancy Testing

Women of childbearing potential are defined as females who are fertile, following menarche and until becoming postmenopausal unless permanently sterile; permanent sterilization methods include hysterectomy, bilateral salpingectomy, and bilateral oophorectomy. A postmenopausal state is defined as amenorrhea for more than 24 consecutive months without an alternative medical cause; women on hormone replacement therapy must have a documented plasma follicle-stimulating hormone level >40 mIU/mL.

Double-blind:

Women of childbearing potential must not become pregnant, and so beginning at menarche must agree to the use of 1 highly reliable method of contraception from 7 days prior to the first dose of study medication until 90 days after the last dose of study medication. Highly reliable contraception methods are defined as those that can achieve a failure rate of $<1\%$ per year; examples of these methods include:

- stable oral, implanted, transdermal, or injected contraceptive hormones associated with inhibition of ovulation, or
- an IUD in place for at least 3 months

Open-label Extension:

Women of childbearing potential must not become pregnant, and so beginning at menarche must agree to the use of 1 highly reliable method of contraception from 7 days prior to the first dose of study medication until 30 days after the last dose of study medication. Highly reliable contraception methods are defined as those that can achieve a failure rate of $<1\%$ per year; examples of these methods include:

- stable oral, implanted, transdermal, or injected contraceptive hormones associated with inhibition of ovulation, or

- an IUD in place for a duration defined as effective in product labeling.

One additional barrier method must also be used during sexual activity from Day 1/Randomization until 30 days after the last dose of study medication. Examples of barrier methods include:

- diaphragm
- diaphragm with spermicide (preferred)
- male partner's use of male condom
- male partner's use of condom with spermicide (preferred)

Serum pregnancy tests will be performed on WOCBP at screening. Urine pregnancy tests will be performed at all other study visits, as well as monthly between visits (see next paragraph). A positive urine pregnancy test during the study must be confirmed with a serum pregnancy test.

Urine pregnancy tests will be dispensed to WOCBP to conduct pregnancy testing at home between study visits, beginning at the Week 12 visit, and continuing through the open-label extension. Patients will receive enough tests to conduct pregnancy testing once monthly until the next scheduled study visit. Sites will contact patients monthly to confirm that the pregnancy test has been performed and the results are negative. If the urine pregnancy test is positive, study medication will be immediately discontinued, and a serum pregnancy test will be performed to confirm the result. If the serum pregnancy test is positive, the Sponsor will be notified, and the patient will be followed to pregnancy outcome as outlined in [Section 10.8](#). At every visit and monthly, sites will verify that WOCBP are continuing to use highly reliable contraception methods as defined in this protocol.

Prior to menarche, pregnancy testing and contraceptive use is not required. However, the patient and their parent/guardian must be advised that immediately upon menarche, the patient will be required to begin pregnancy testing and initiate contraceptive use. Upon menarche, study medication should be stopped until highly reliable contraception per protocol specifications has been started and is considered to be effective. These requirements cannot be avoided.

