7. Women of childbearing potential (WOCBP), beginning at menarche, must agree to the use of 1 highly reliable (ie, can achieve a failure rate of $< 1\%$ per year) method of contraception from 7 days prior to the first dose of study medication until 90 days after the last dose of study medication. Examples of highly reliable contraception methods include stable oral, implanted, transdermal, or injected contraceptive hormones associated with inhibition of ovulation, or an intrauterine device (IUD) in place for at least 3 months. One additional barrier method must also be used during sexual activity, such as a diaphragm or diaphragm with spermicide (preferred), or male partner's use of male condom or male condom with spermicide (preferred), from Day 1/Randomization until 90 days after the last dose of study medication. WOCBP are defined as those who are fertile, following menarche and until becoming postmenopausal unless permanently sterile; permanent sterilization methods include hysterectomy, bilateral salpingectomy, and bilateral oophorectomy. A postmenopausal state is defined as amenorrhea for more than 24 consecutive months without an alternative medical cause; women on hormone replacement therapy must have a documented plasma follicle-stimulating hormone level > 40 mIU/mL. All WOCBP must have a negative serum pregnancy test at Screening (Visit 1), and a negative urine pregnancy test, with positive results confirmed by serum, at every study visit from Randomization (Visit 3) and after.
NOTE: Prior to menarche, pregnancy testing and contraceptive use are not required. However, the patient and their parent/guardian must be advised that, immediately upon menarche, the patient will be required to begin pregnancy testing and initiate contraceptive use. This requirement cannot be avoided.

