Quantitative Urinalysis (1 first morning void) ^g		X	X	X	X	X	X
Routine Urinalysis		X	X	X	X	X	X
QoL Questionnaire ^h		X	X	X	X	X	X
Urine Pregnancy Test ⁱ		X	X	X	X	X	X
Dispense Urine Pregnancy Tests ⁱ		X	X	X	X	X	X
Biorepository Samples (blood and urine, if consented)		X	X	X	X	X	X
Medication Dispensing ^j	X	X	X	X	X	X	X
Medication Accountability		X	X	X	X	X	X
Adverse Event Assessment	-----Continuous Monitoring -----						
Concomitant Medications/Therapies	-----3 Months Prior to Screening Followed by Continuous Monitoring -----						

ALP = alkaline phosphatase; ALT = alanine aminotransferase; AST = aspartate aminotransferase; BUN = blood urea nitrogen; eGFR = estimated glomerular filtration rate; EQ-5D = EuroQoL, 5-dimension QoL instrument; HDL = high-density lipoprotein; KDQOL = Kidney Disease Quality of Life instrument; LDL = low-density lipoprotein; MCH = mean corpuscular hemoglobin; MCHC = mean corpuscular hemoglobin concentration; MCV = mean corpuscular volume; NT-proBNP = N-terminal prohormone of brain natriuretic peptide; PedsQL = Pediatrics Quality of Life Inventory; QoL = quality of life; RAAS = renin-aldosterone-angiotensin; WBC = white blood cell; WOCBP = women of childbearing potential

^a Informed consent for participation in the open-label period (either at Study Visit Week 108 or Study Visit Week 112) must be obtained prior to any assessment or study medication administration.

^b Physical examinations will include assessment of the following body systems: abdomen; cardiovascular; ear, nose, and throat; eyes; hair and skin; lymph nodes; mental status; musculoskeletal; neurological; peripheral edema; and respiratory. Peripheral edema will be assessed using the semi-quantitative scale shown in Appendix B (Section 15.2.3).

^c Vital signs will always be measured prior to having blood drawn for laboratory evaluations. Blood pressure will be measured after patients have been sitting comfortably in a chair for at least 5 minutes prior to obtaining 3 readings using the same arm for each reading; the mean of the last 2 readings will then be recorded. Measurements of blood pressure intended to detect possible orthostatic hypotension will also be performed at each visit (see Section 9.6). For these measurements, blood pressure will be measured 3 times: 1 time after the patient has been in a supine position for 5 minutes, 1 time after the patient has been

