standing for 1 minute, and 1 time after the patient has been standing for 3 minutes. Weight, heart rate, temperature, and respiration rate will also be recorded. For patients <18 years of age, height will be measured every 6 months until the patient turns 18.

- ^d Except for Week 114 (see footnote e), Includes clinical chemistry (sodium, potassium, chloride, bicarbonate, total protein, albumin, calcium, phosphate, glucose, cystatin, uric acid, BUN, creatinine [including calculation of eGFR], bilirubin [total, direct, and indirect], ALT, AST, ALP, gamma glutamyl transferase, creatine kinase, and amylase); lipid panel (total cholesterol, LDL [direct], HDL [direct], and triglycerides [direct]); hematology (red blood cells, hemoglobin, hematocrit, MCV, MCH, MCHC, platelets, WBC and WBC differential [neutrophils, eosinophils, basophils, lymphocytes, and monocytes, % and absolute]). All chemistry, hematology, and lipid analytes are shown in [Section 15.2.4](#).
- ^e Includes only serum creatinine and serum potassium.
- ^f NT-proBNP in patients ≥ 18 years of age only.
- ^g Urine total protein, creatinine, and microalbumin. The patient will collect the first morning void within 5 days prior to the visit and bring the sample to the site visit.
- ^h Patients ≥ 18 years of age will complete the KDQOL instrument, and patients <18 years of age will complete the PedsQL QoL questionnaire. All patients will also complete the EQ-5D. If the questionnaires were NOT completed at Week 112 (ie, Visit 17), the patient should not complete them for the rest of the open-label extension.
- ⁱ Urine pregnancy tests will be dispensed to WOCBP to conduct pregnancy testing at home between study visits. Site will provide the patient enough tests to conduct pregnancy testing once per month until the next scheduled study visit and will contact these patients monthly to confirm that the pregnancy test has been performed and the results are negative. A positive urine pregnancy test will be confirmed by a serum test. At every visit and monthly, sites will verify that WOCBP are continuing to use highly reliable contraception methods.

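### Table 6 marks no urine pregnancy test and no home-test dispensing at Week 114, contrary to Section 9.9 and criterion 7, and the supply rule does not assure monthly home tests from Week 114 to Week 124

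*Protocol*

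**What the plan says.** All references are to the Protocol.

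- **Section 9.9, visit testing.** After the serum test at screening, "Urine pregnancy tests will be performed at all other study visits, as well as monthly between visits". The sentence follows the open-label paragraphs of that section and is not limited to the double-blind period.
- **Section 7.1.1, criterion 7.** Women of childbearing potential must have "a negative urine pregnancy test, with positive results confirmed by serum, at every study visit from Randomization (Visit 3) and after".
- **Section 9.9, home testing.** Home tests are handed out "beginning at the Week 12 visit, and continuing through the open-label extension". On quantity: "Patients will receive enough tests to conduct pregnancy testing once monthly until the next scheduled study visit". On follow-up: "Sites will contact patients monthly to confirm that the pregnancy test has been performed and the results are negative".
- **Section 15.1, Table 5, Week 112.** A urine pregnancy test is marked. Home-test dispensing is also marked, with a footnote limiting it to patients who enter the extension.
- **Section 15.1, Table 6.** Week 114 is Visit 18. The urine pregnancy test row and the row "Dispense Urine Pregnancy Tests" are both empty at Week 114 and marked at the other six visits, from Week 124 on.
- **Footnote h (Table 5) and footnote i (Table 6).** Both repeat the supply rule: "Site will provide the patient enough tests to conduct pregnancy testing once per month until the next scheduled study visit".

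**The concern.** A site cannot follow both the text and Table 6 at Week 114. The text calls for a urine test at that visit; the table marks none, and no footnote or paragraph exempts the visit.

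The supply rule adds a second problem. It sizes each issue of home tests to the next scheduled visit. After Week 112 that visit is Week 114, only two weeks later, and Table 6 then issues no tests until Week 124. Section 9.9 still requires a monthly test and a monthly call to confirm it, so the site must confirm tests whose supply the schedule does not clearly provide.

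The timing matters. Section 4.1 states that endothelin receptor antagonists are expected to harm the fetus. Open-label sparsentan starts at Week 112, and for patients randomized to irbesartan this is their first exposure, since exclusion criterion 20 bars earlier sparsentan use. Week 114 is the visit at which tolerability is judged and the dose may be raised. Table 6 dispenses study medication at Week 114 but no pregnancy tests.

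**Working it through.** The plan states no figure for this interval, so there is none to reproduce. The check compares table cells with text and then does visit-window arithmetic.

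**1. Is the blank cell real?** Table 6 has seven visit columns (Weeks 114, 124, 136, 148, 160, 172, 184). Physical examination, vital signs and medication dispensing carry seven marks each. The two pregnancy-test rows carry six, with the first cell empty. The blank is therefore in the table and not a product of text extraction.

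**2. Comparable visit in the double-blind period.** Week 2 is also the tolerability and titration visit after two weeks on the initial dose. Table 4 marks a urine pregnancy test there, and at Weeks 4, 6, 8 and 12.

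**3. Inputs (Tables 5 and 6).**

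| Visit | Window | Earliest week | Nominal | Latest week |
|---|---|---|---|---|
| Week 112 | −7 to +14 days | 111 | 112 | 114 |
| Week 114 | ±2 weeks | 112 | 114 | 116 |
| Week 124 | ±4 weeks | 120 | 124 | 128 |

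**4. Interval between marked on-site tests (Week 112 to Week 124).**

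- Nominal: 124 − 112 = 12 weeks (84 days)
- Longest: 128 − 111 = 17 weeks (119 days)
- Shortest: 120 − 114 = 6 weeks

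**5. Interval with no dispensing after the literal end of the Week 112 supply (Week 114 to Week 124).**

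- Nominal: 124 − 114 = 10 weeks
- Longest: 128 − 112 = 16 weeks

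**6. Home tests needed at one per month.** One month = 365.25 / 12 / 7 = 4.35 weeks. The number of tests is the interval divided by 4.35, rounded down.

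| Interval | Weeks | Monthly home tests |
|---|---|---|
| 112 to 114, nominal | 2 | 0 |
| 112 to 114, longest (116 − 111) | 5 | 1 |
| 114 to 124, nominal | 10 | 2 |
| 114 to 124, longest | 16 | 3 |
| 112 to 124, nominal | 12 | 2 |
| 112 to 124, longest | 17 | 3 |

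Read literally, the supply rule asks for 0 or 1 test at Week 112, whereas monthly testing to Week 124 takes 2 or 3. The difference is supply that the documents do not assure. It is not a count of tests that will be missed.

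**The case against.** The strongest reply is that testing does not stop. Table 5 marks both a test and home-test dispensing at Week 112 for extension entrants. Monthly home testing with monthly site contact continues through the extension (Section 9.9, repeated in Section 10.8), so a site would probably notice a missing kit at its first monthly call. Issuing monthly tests for a two-week interval makes little sense, so the Week 112 supply may well be meant to last to Week 124. Week 114 is a limited visit: its laboratory work is creatinine and potassium only, and urinalysis, quality of life and medication accountability are also blank. Other safeguards apply: the Week 112 evaluations precede the first open-label dose, pregnancy excludes entry to the extension (Section 7.2.2), and highly reliable contraception plus a barrier method is required.

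Most of this stands, and it defeats two stronger inferences that a reader might draw.

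- **That women have no scheduled or supplied test for 12 to 17 weeks.** The documents do not support this. Those figures are intervals between marked on-site tests, and home tests are both dispensed at Week 112 and required monthly.
- **That two or three tests are missed per woman.** This would hold only if sites applied the supply rule literally and also ignored the monthly testing and contact requirements.

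The reply does not remove the contradiction at Week 114. A deliberately reduced visit would explain the blank cells, but nothing in the text says so. The longer reading of the Week 112 supply is sensible, but it is not what the supply rule states.

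**Conclusion.** The inconsistency is real and should be corrected. Table 6 conflicts with Section 9.9 and criterion 7 at Week 114. As a result no on-site test is marked for 12 weeks nominally (6 to 17 with windows). Supply of the required monthly home tests is not assured from Week 114 to Week 124, which is 10 weeks nominally and up to 16.

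The upper figures assume that one visit falls at the early edge of its window and Week 124 at the late edge; they are limits, not typical values. The supply conclusion rests on reading the next scheduled visit after Week 112 as Week 114, which is how Table 6 lists it. A site that issues enough tests at Week 112 to reach Week 124 closes the supply gap, although the on-site contradiction remains. This review takes no position on whether the text or the table has the right testing schedule.

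**What to change.** Reconcile Section 9.9, criterion 7, Table 5 (footnote h) and Table 6 (footnote i) so that text and tables agree on pregnancy testing at Week 114. Whichever way that is settled, make the dispensing entries and the supply rule cover the required monthly home tests through the Week 124 visit, including its +4-week window. On the arithmetic above, that is 2 home tests nominally and 3 at the longest interval.

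The cost is a table or text correction and a few urine test kits per woman of childbearing potential. No visit is added.

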9.10. Patient-reported Outcomes

The following PROs will be used to evaluate the effects of sparsentan (as compared to irbesartan) on improvements in health-related QoL:

- Patients ≥ 18 years of age:
 - Kidney Disease Quality of Life (KDQOL) instrument
 - EuroQol, 5-dimension QoL instrument, version 5L (EQ-5D-5L)
- Patients < 18 years of age:
 - Pediatric Quality of Life Inventory (PedsQL) questionnaire. The PedsQL instrument consists of 2 developmentally appropriate modules; the Child Self-Report for ages 8-12 and Child Self-Report for ages 13-18.
 - EuroQol, 5-dimension QoL instrument, version Y (EQ-5D-Y).

If the questionnaires were NOT completed at baseline of the double-blind period (ie, Day 1), the patient should not complete them for the rest of the double-blind period. Patients participating in the open-label extension who did not complete the questionnaires at Day 1 should complete them at Week 112 (as baseline assessments for the open-label extension) and through the Week 268/End of Study visit. If the questionnaires were not completed at Week 112, the patient should not complete them for the rest of the open-label extension. Once a patient enters the open-label extension portion of the study, questionnaires will continue to be collected through the Week 268/End of Study visit.

9.11. Pharmacokinetic Assessments

Samples enabling assessment of sparsentan and irbesartan in plasma will be taken during the double-blind period according to the schedule of study events in [Section 15.1](#). At applicable visits, 1 sample will be taken pre-dose in the clinic.

9.12. Biorepository Samples

With patient consent (or assent as appropriate), serum, plasma, and urine samples will be collected for assessment of biomarkers that could help better understand the mechanisms of disease and treatment. Additional biomarkers may be identified during or after the study and be considered for assessment in the future.

Samples will be collected at visits specified in the schedule of events during both the double-blind- and open-label periods of the study, as specified in [Section 15.1](#).

Patients may withdraw consent for use of biorepository samples at any time, as described in the ICF. Biorepository samples will not be used for genetic testing. Samples will be shipped and stored according to instructions in the Laboratory Manual. The samples will be destroyed 5 years after the clinical study report is finalized.

9.13. Genotyping

Blood samples for genotyping of FSGS and nephrotic syndrome-associated genes, and apolipoprotein1 polymorphisms will be taken at Day1/Randomization. Test results, if available, may be provided to Investigators after study completion. Samples will be used only for this purpose and will be destroyed once the sample analysis is complete.

9.14. Safety Assessments

The safety and tolerability of sparsentan will be evaluated by AEs and by vital signs, physical examinations, clinical laboratory parameters, and 12-lead ECGs.

10. ADVERSE EVENT REPORTING

10.1. Adverse Event (AE)

An AE is any untoward medical occurrence associated with the use of the study medication (active or placebo, biologic, or device) in a clinical investigation patient, but does not necessarily have a causal relationship with the study medication. An AE can, therefore, be any unfavorable and unintended sign (eg, an abnormal laboratory finding), symptom, or disease temporally associated with the use of a study medication, whether or not considered related to the study medication.

Adverse events may include:

- Symptoms described by the patient
- Clinically significant changes in the patient's physical examination or other signs observed by the Investigator or medical staff
- Test abnormalities (laboratory tests, ECG, X-rays, etc.) that reflect a change from baseline (Day 1 for the double-blind period or Week 112 for the open-label extension) and/or that may result in changes in administration of study medication or in an alteration in medical care (diagnostic or therapeutic)
- Conditions present at baseline (Day 1 for the double-blind period or Week 112 for the open-label extension) that have either worsened or recurred following resolution

The patient will be evaluated for new AEs and the status of existing AEs at each study visit, including screening or washout periods, or at any time contact is made with the patient outside of a scheduled visit. The Investigator may elicit symptoms using an open-ended question, followed by appropriate questions that clarify the patient's verbatim description of AEs or change in concomitant medications.

10.1.1. COVID-19 Adverse Events

If a patient is diagnosed with COVID-19 by a positive test result and any of the SAE criteria (Section 10.2) are met, report the event as an SAE. If a patient has a positive test result for COVID-19 and is asymptomatic, or is symptomatic but not meeting SAE criteria, it should be reported as an AE.

As with all SAE reporting, the SAE should be reported, per protocol, within 24 hours of becoming aware of the event. If the 24-hour reporting deadline is not met, then a note should be added to the SAE Report Form stating the reason the timeline was not adhered to.

10.2. Serious Adverse Event (SAE)

An SAE is an AE that results in any of the following:

- Death: The patient died as the result of the event.
- Is life-threatening: An AE that places the patient, in the view of the Investigator or the Sponsor, at immediate risk of death from the AE as it occurred; ie, does not include an AE that, had it occurred in a more severe form, might have caused death.

- Requires in-patient hospitalization or prolongation of an existing hospitalization:
Note: Planned or elective hospital admissions for treatment/procedures for a condition/disease that existed prior to signing the informed consent will be recorded in the patient's screening documents and will not be captured as SAEs. If, however, the admission or procedure occurs other than planned due to a worsening of the condition, the event will be recorded as an SAE.
- Persistent or significant disability/incapacity: An AE that results in a substantial disruption of a person's ability to conduct normal life functions.
- Congenital anomaly/birth defect: A congenital anomaly/birth defect that occurs in the offspring of a patient exposed to the study medication.
- Other medically important serious events: An AE that may not result in death, be life-threatening, or require hospitalization may be considered an SAE when, based upon appropriate medical judgment, the event may jeopardize the patient and may require medical or surgical intervention to prevent one of the outcomes listed above.

Voluntary admission to the hospital (eg, for elective surgery) will not be considered an SAE.

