6.1.1.3. Exploratory Endpoints for the Double-Blind Period

- The slopes of eGFR over approximately 1 year of randomized treatment evaluated following the initial acute effect of randomized treatment (ie, from Week 6 to Week 60; chronic slope over 1 year) and after initiation of randomized treatment (ie, from Day 1 to Week 60; total slope over 1 year)
- The absolute and percent change from baseline of the double-blind period in eGFR at each visit
- The percent change from Week 6 in eGFR at each visit
- The proportion of patients achieving a UP/C ≤ 1.5 g/g (170 mg/mmol) and a $>40\%$ reduction from baseline of the double-blind period in UP/C at each visit

- The percent change from baseline of the double-blind period in UP/C at each visit
- The time to achieve the target reduction in UP/C (ie, ≤ 1.5 g/g [170 mg/mmol] and a $>40\%$ reduction)
- The proportion of patients reaching a confirmed 40% reduction in eGFR, ESRD, or death. (ESRD is defined as initiation of RRT or sustained eGFR <15 mL/min/1.73 m² during the study).
- The proportion of patients reaching a confirmed 30% reduction in eGFR, ESRD, or death
- Changes from baseline of the double-blind period in blood pressure at each visit
- The proportion of patients requiring initiation of or intensification in immunosuppressive medication during the study
- The proportion of patients undergoing reduction in immunosuppressive medication during the study
- The time to initiation or intensification of immunosuppressive medication during the study
- Changes from baseline of the double-blind period in quality of life (QoL), measured via patient-reported outcome (PRO) at each visit beginning with Week 12
- Frequency and duration of hospitalizations (for any reason and for reasons related to the kidney)
- Trough plasma PK concentrations during the double-blind period

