10.5. Serious Renal Conditions

The following conditions should always be reported as SAEs:

- Progression of CKD leading to chronic dialysis: For patients who undergo transition to chronic maintenance dialysis, the verbatim SAE term should be reported as “progression of CKD leading to chronic dialysis.” The term “chronic dialysis” should also be captured on the Concomitant Procedure page of the eCRF.
- Medical conditions requiring transient acute dialysis: For patients who undergo transient acute dialysis, the verbatim SAE term should record the condition for which the dialysis is required. For example, if a patient requires acute dialysis due to hyperkalemia, the verbatim SAE term would be reported as “hyperkalemia requiring transient acute dialysis.” The “acute dialysis” should also be captured on the Concomitant Procedure page of the eCRF.
- Kidney transplantation: For patients receiving a kidney transplant, the reason for the transplant should be recorded as the verbatim SAE (eg, “progression of CKD requiring kidney transplant”). The term “kidney transplant” should also be captured on the Concomitant Procedure page of the eCRF.

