10.7. Reporting Adverse Events and Serious Adverse Events

10.7.1. Reporting Adverse Events

Adverse events (including SAEs) will be captured from the time informed consent is signed to the patient's final visit.

For patients who prematurely discontinue study treatment (see [Section 8.3.2](#)) but who are not withdrawn from the study, AEs will continue to be recorded until the patient completes the study (see [Section 6.3.1](#) for definition of patient completion).

If a patient initiates RRT after premature discontinuation of study treatment, only AEs and SAEs considered related or possibly related to study treatment need to be recorded.

Adverse events will be recorded using appropriate medical terminology. When recording, it is preferable to provide a diagnosis. In the absence of a diagnosis, each sign and symptom will be captured as a unique AE. Sufficient information should be sought to assist the Investigator both in determining the diagnosis and in making a causality assessment.

Reporting should not be delayed pending receipt of all required information. If information is unavailable at the time of the initial report, the Investigator is expected to follow-up until the required information has been obtained.

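### The closing sentence of Protocol 10.2 exempts elective admissions from SAE status without the pre-consent limit set by the Note above it, so an elective admission for a new on-study event can be classified both ways.

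*Protocol*

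**What the plan says.** Protocol Section 10.2 defines an SAE as an AE with one of six results. One of them is: "Requires in-patient hospitalization or prolongation of an existing hospitalization". The Note under that bullet removes a limited class from SAE capture: "Planned or elective hospital admissions for treatment/procedures for a condition/disease that existed prior to signing the informed consent". Such admissions go in the screening documents instead. The Note then takes back part of the exemption: "If, however, the admission or procedure occurs other than planned due to a worsening of the condition, the event will be recorded as an SAE".

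After all six criteria, Section 10.2 ends with a free-standing sentence: "Voluntary admission to the hospital (eg, for elective surgery) will not be considered an SAE". It says nothing about when the condition arose or whether it worsened.

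Section 10.5 lists progression to chronic dialysis, conditions needing transient acute dialysis, and kidney transplantation, under the lead-in "The following conditions should always be reported as SAEs". For transplantation it adds: "Kidney transplantation: For patients receiving a kidney transplant, the reason for the transplant should be recorded as the verbatim SAE". It makes no exception for scheduled admissions.

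**The concern.** A seriousness definition should give one answer for a foreseeable case. Here a site that applies the hospitalisation criterion and the Note will report an elective admission for a new on-study condition as serious, and a site that applies the last sentence will not. Both can point to the protocol. The study plans approximately 300 centres, so different readings are a practical possibility.

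SAE status has consequences that ordinary AE status lacks:

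- **Expedited reporting.** Section 10.7.2 requires SAEs to reach the sponsor within 24 hours of the investigator's first knowledge.
- **Follow-up.** Under Section 10.7.3, follow-up of a non-serious AE may end when the patient's participation ends. An SAE is followed until it resolves or stabilises, or until investigator and sponsor agree to stop.
- **Safety oversight.** Section 13.2 has the DMC review narratives of interval SAEs and a cumulative SAE list. Hospitalisations as such are not in its stated minimum data.
- **Safety tables.** SAP Section 10.1 tabulates serious TEAEs by system organ class and preferred term. SAP Sections 10.1 and 10.1.2 do so again for the safety topics of interest.

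**Working it through.** The plan states no figure on this point and no arithmetic applies. The check is to take each type of admission through the criterion and Note of Section 10.2, its closing sentence, and Section 10.5.

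1. **Elective admission for an AE first arising after consent.** Criterion: SAE. Note: no exemption, because the condition did not exist before consent. Closing sentence: not an SAE. *The texts conflict.*
2. **Elective admission newly scheduled on study because a pre-consent condition has worsened.** The first part of the Note could exempt it, since the condition pre-dates consent and the admission is elective. The second part could bring it back, if a newly arranged admission counts as other than planned. The instruction to record exempt admissions in the screening documents suggests the Note means admissions already known at screening, but it does not say so. Closing sentence: not an SAE. *The text is ambiguous.*
3. **Scheduled admission for kidney transplant or to start chronic dialysis.** Section 10.5: always an SAE. Closing sentence read literally: not an SAE. *The wording conflicts*, but the more specific rule with 'always' would reasonably govern.
4. **Unplanned admission because a pre-consent condition has worsened.** Note: SAE. Closing sentence: not engaged, since the admission is neither voluntary nor elective. *No conflict.*
5. **Emergency or other non-elective admission for a new condition.** Criterion: SAE. Closing sentence: not engaged. *No conflict.*
6. **Elective admission for an unchanged pre-consent condition.** Note and closing sentence agree: not an SAE. *No conflict.*

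Case 1 is a true contradiction, case 2 an ambiguity, and case 3 a verbal clash that Section 10.5 can be read to settle. The other three are sound.

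Other provisions do not restore SAE status in case 1. Under Section 10.7.1, "Adverse events (including SAEs) will be captured from the time informed consent is signed", so the event itself is recorded, but possibly only as non-serious. The medically important criterion in Section 10.2 is discretionary: it says such an event may be considered serious, not that it is.

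**The case against.** The best defence is that the sentences can be read together. An SAE is an AE that requires hospitalisation, and an admission that an AE requires is not naturally called voluntary. On that reading the closing sentence does something the Note does not: it covers admissions with no untoward event behind them, such as elective sterilisation or cosmetic surgery. This is a fair reading, and the replacement text should preserve that function. It does not remove the problem, because the sentence gives elective surgery as its example, and surgery for a condition that arose on study can be both elective and required by an AE. Nothing in the sentence tells a site to exclude that case.

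Several stronger readings are tempting and are not supported:

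- *Hospitalisations for new or worsened conditions drop out of the SAE data generally.* They do not. Non-elective admissions are untouched, and the Note expressly keeps unplanned admissions due to worsening.
- *Transplant and dialysis events are lost.* This does not follow. A site following Section 10.5 reports them.
- *The safety record or the DMC is blind to these events.* The event is still an AE and may be serious under another criterion. Section 13.2 also gives the DMC coded AEs and AEs leading to early withdrawal of study medication, and lets it request unblinded individual data.
- *The hospitalisation endpoint is compromised.* Protocol Section 6.1.1.3 defines it as "Frequency and duration of hospitalizations (for any reason and for reasons related to the kidney", and neither Protocol Section 12.7.3 nor SAP Section 8.8.6 attaches an SAE condition. No further statement is needed there.
- *The loss differs between arms.* The documents contain nothing from which to infer this.

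**Conclusion.** The point holds in limited form. The closing sentence of Section 10.2 is wider than the Note it follows, and for an elective admission prompted by an AE that first arises on study the section gives two opposite answers. For an elective admission newly arranged because a pre-consent condition worsened, the answer is unclear. For scheduled transplant or dialysis starts there is a clash of wording that 'always' in Section 10.5 would reasonably resolve.

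The consequence is possible inconsistent SAE classification of elective on-study admissions, carried into expedited reporting, follow-up, DMC narratives and the serious TEAE tables. Its size is unknown: the documents give no hospitalisation rate and no share of admissions that are elective. The primary, surrogate and secondary efficacy analyses do not depend on it. The conclusion assumes only that some sites would apply the closing sentence as written. It is worth correcting because the rule, followed literally, misclassifies events and the correction is cheap.

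**What to change.** Replace the closing sentence of Section 10.2 with:

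> A voluntary or elective admission is not an SAE when there is no underlying AE, or when it is for a condition that existed before consent and has not worsened (see Note). An AE that arises or worsens after consent and requires in-patient admission is an SAE even if the admission is scheduled, and events in Section 10.5 are always SAEs.

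The first clause matters. If the exemption covered only pre-consent conditions, an elective admission with no untoward event behind it would become an SAE, contrary to the section's own premise that an SAE is first an AE.

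Send sites a short reminder asking them to recheck elective on-study admissions already recorded as non-serious.

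The cost is a two-sentence replacement in a protocol amendment, the site recheck, and slightly more SAE forms.
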